- b. **Vital Signs, Weight and Height:** Baseline vital signs, bladder scan, weight and height are measured at the start of the study visit. Vital signs and weight measurements are repeated at the end of the study visit.
- c. **Pregnancy Testing:** A point-of-care pregnancy test is performed for women under the age of 65 who have not had a hysterectomy.
- d. **IV Line Placement & Patient Acclimation**
 - 1. **IV Line Placement:** A peripheral IV line is placed as part of the Standard of Care for receiving IV diuretics during admission at YNHH. If a suitable IV for the blood volume procedure is not available, one will be placed.
 - 2. **If a KVO is required to keep the IV line patent, Dextrose 5% fluid will be used.**
- e. **Acclimation:** Patient rests in a semi-recumbent position for approximately 60 minutes prior to undergoing blood volume determination and randomization.
- f. **Screening:** After the peripheral IV line is placed, blood will be drawn for determination of venous pH via iSTAT and/or YNHH laboratory. If the patient's venous pH is less than 7.25, they will be withdrawn from the study.
- g. **Patients will receive one of the following tracers depending on availability:**
 - 1. Iothalamate Administration
 - 1 IV iothalamate: 1 cc of Iothalamate meglumine is administered intravenously in patients without a contrast allergy
 - 2 Iohexol Administration
 - 2 IV Iohexol: 1 cc of Iohexol will be administered intravenously in patients without a contrast allergy

i. Volumex Administration and Daxor Blood Volume Sample Collection

i.1 **Baseline Blood Collection:** Blood is collected prior to the Volumex injection to establish a baseline that reflects background radiation.

i.2 **Volumex Injection:** Up to 25 microcuries of the Volumex tracer (radiolabeled albumin) is injected as an intravenous bolus (IV-push).

i.3 **Blood Volume Serial Blood Collection** A series of 5 postVolumex blood samples is collected after tracer injection, allowing for complete mixing in the bloodstream.

i.4 **Blood Volume Sample Timing:** Samples are ideally spaced ~6 minutes apart, and are collected approximately 12, 18, 24, 30 and 36 minutes after Volumex administration. Dextrose 5% fluid will be used to flush the IV line with administration of Volumex and in between blood draws for the blood volume.

- ii. **Standard YTCC or Inpatient IV Diuretic Therapy Protocol** **ii.1** The IV diuretic therapy prescribed by their treating clinician if inpatient.

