 - The participant will be instructed to inform their treating physician when inpatient and the study team (if discharged) of any abdominal upset, the Imodium will be built into the epic order set(PRN order) for the care team to administer. If the patient is discharged, the PI or sub- I will be notified, and it is deemed appropriate; The study team will provide the participant with the Imodium.
 - The participant will be assessed daily for additional or worsening unformed stools, if appropriate the patient will receive additional doses of Imodium according to the manufacturer's instructions in conjunction with approval from the treating physician(inpatient) or study PI or sub- I if (discharged).

- Imodium over the counter: initial: Take 2 tablets/ capsules (4 mg) once. May take 1 additional tablet/ capsules after another episode of unformed stool. Up to a maximum of (8) 2 mg tablets or capsules or 16mg daily.
- The study team will provide the over the counter Imodium (once the patient is discharged) and the study team will record the number of doses taken per day

Patient Discharge vi.1 Vital Signs: Vital signs are obtained at the end of the study visit prior to discharge, to ensure patient safety.

vi.2 Home Urine Collection: patients will be given 24-hour urine collection containers to continue collecting urine at home.

B: Daily Monitoring and Dose Adjustment If a patient has a serum bicarbonate level less than 22mmol/L at screening, a venous pH and basic blood chemistries will be obtained via iSTAT and/or YNHH laboratory each day during the study period. 1cc of blood will be drawn each day to perform the test. If the patient has been discharged from YNHH and these tests are indicated, additional safety visits will take place (up to 5). For all patients, the results of any safety tests will be reviewed by the study physician and study nephrologist ([name]). If necessary, the study drug dose will be adjusted to once daily or no doses. The standard dosage is twice a day.

C: Continued IV Diuretic Therapy: The patient will remain admitted until the treating practitioner feels the patient no longer requires IV therapy, at which point they will be transitioned to oral diuretics.

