D: Transition to Oral Diuretics: Upon transition to oral diuretics, the patients will be seen every other day (except for weekends) for laboratory monitoring of electrolytes and renal function. 10cc of blood will be drawn at each of these safety visits (which are separate from the additional safety visits that will be conducted based on serum bicarbonate), and a urine sample will also be collected.

E: Study Visit 2: After 7 days of randomized therapy (5-8 to minimize missing data), the patient will return or if still admitted have repeat blood volume assessment and bio-samples collection. The number of days of randomized therapy may be less than 5 days in order to allow for the completion of the visit 2 while the patient remains hospitalized, this would be utilized only during times of a pandemic or when there is an reduced visit capacity.

Patients enrolled into the open-label arm will return after 7 days of therapy with lysine chloride (5-8 to minimize missing data).

F: Follow Up Visit/ Phone Call: One week after the completion of Visit 2, subjects will be given the option to either come in for a follow up visit or complete a follow up phone call. The purpose of this follow up visit is to make sure they are not experiencing any side effects or adverse events after taking the study medication/placebo as well as obtain a current weight, vital signs, a 10cc blood sample and a urine sample. If the subject is not able to come in for the follow up visit, a follow up phone can be done in its place. During the phone call, the subject will be asked their current weight, how they are feeling and will be assessed for any adverse events.

G: Study Locations: This is a multi-site study. Depending on space availability and other logistics, the patient may be asked to complete any daytime study procedures (either study visits or follow up visits) at either the YNHH Hospital Research Unit

(HRU), at the research group's outpatient clinic space at [name], or at St. Francis Hospital. The St. Francis site will seek IRB approval from their local IRB.

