7.4 Subject Inclusion and Exclusion Criteria

Inclusion Criteria

- a. Clinical diagnosis of decompensated heart failure with at least one objective sign of volume overload (rales, edema, elevated JVP, or weight gain of at least 5 pounds)
- b. A projected need by the treating clinician for continued treatment with IV diuretics
- c. Chronic loop diuretic use **OR** no chronic loop diuretic use and serum chloride <100 mmol/l
- d. 18 years old

Exclusion Criteria

- a. Inability to commit to or comply with serial visits
- b. History of severe metabolic or respiratory acidosis within 30 days of enrollment
- c. Use of metformin, acetazolamide, or any other agent that could predispose to acidosis. Patients who are on metformin may be enrolled if their metformin can

be discontinued safely for the duration of the study. Any participants who have consistently elevated Blood glucose readings > 200 mg/dL while inpatient will not be enrolled.

- d. Serum bicarbonate level < 20 mmol/L
- e. Estimated glomerular filtration rate < 20 mL/min or renal replacement therapy
- f. Urine output of < 500 mL/24 hours despite use of IV loop diuretic therapy
- g. Appears unlikely, or unable to participate in the required study procedures, as assessed by the study PI or research RN (ex: clinically-significant psychiatric, addictive, or neurological disease)
- h. Inability to give written informed consent or follow study protocol

Exclusion criteria for randomization:

Prior to randomization, a venous pH level will be determined. If the venous pH is less than 7.25, the patient will not be randomized.

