- f. **Lysine Chloride:** Lysine Chloride is freely available to the public as a dietary supplement and food additive and is on the FDA Generally Recognized as Safe (GRAS) list. Every day we eat large quantities of lysine and chloride in our diet. No significant side effects are anticipated to occur from lysine chloride based on a multitude of animal and human studies done with this supplement and the brevity of this intake (8 days). There was a rare incidence of minor GI upset associated with taking lysine chloride as a supplement in some of these studies, including nausea, abdominal pain and diarrhea. However, no side effects necessitating the discontinuation of lysine chloride supplementation were reported.^{a, b, c, d} This research group previously performed a preliminary study with 11 patients involving supplementation of lysine chloride at 21 grams per day, with no adverse events reported (HIC #1308012508, minimal risk study). The doses of lysine chloride

administered in this study are higher than the majority of prior studies, which did not study patients with heart failure. As a result, new, unexpected, or exaggerated side effects are possible.

- i. **Acidosis:** One possible side effect that we will follow closely will be the buildup of acid in the patients' blood, a condition that in very severe cases can cause illness or even be fatal. This condition would slowly develop if it were to happen and thus we will closely monitor serum pH and bicarbonate over the course of the study to be sure this does not occur. Importantly, we did not see any evidence of acid buildup in our pilot study of heart failure patients where similar doses were used.
- ii. **Volume depletion:** An additional possibility is that lysine chloride will work "too well" in removing fluid which could cause dehydration and possible kidney damage. As a result, we will closely follow kidney function throughout the course of the study and adjust diuretics dosage and the study medication if too much fluid is removed.

References

- a. Rubin, A.L., et al., The Use of L-Lysine Monohydrochloride in Combination with Mercurial Diuretics in the Treatment of Refractory Fluid Retention. *Circulation*, 1960. 21(3): p. 332-336.
- b. Spencer, H., Samachson, J., 1963. Effect of lysine on calcium metabolism in man. *J. Nutr.* 81:301-6.

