8.3 Minimizing Risks

- a. **Data collection:** Identifying data will be available only to the study PI and study coordinator, and will be used only to facilitate medical record review, and prevent duplicate screenings of patients while looking for subjects to enroll in the study. All data sheets, electronic data entries, and laboratory samples will be labeled with a unique identifier code. These numbers will be unique to the patient and will be the common link between specimens and the data. No identifying data will be reported to the public or in any publications that may result from this research.
- b. **Emotional, psychological, economic risk:** Blood samples will be drawn off of the IV line to reduce patient discomfort, and to avoid the patient being subjected to multiple straight needle sticks.
- c. **Urine collection and bladder scanning:** Collecting urine and performing bladder scans during the study presents minimal risk to the patient.
- d. **IV Insertion & Blood draws:** The risks of blood draws will be minimized by drawing the minimum volume necessary for study purposes. The risks of pain and infection will be minimized by having blood drawn by qualified, experienced staff who have achieved competency with phlebotomy. All standard precautions will be maintained during the procedure. Patients' discomfort will be minimized by drawing blood from the IV line when possible, instead of subjecting the patient to multiple straight sticks.
- e. **IV drug administration:** Injections will be performed by qualified, experienced staff who have demonstrated competency with the technique. The sterility of the IV line will be diligently maintained by research staff to help prevent infections. Sites will be closely monitored for warmth, redness, swelling, pain and leaking. The IV line will be flushed before and after each medication is administered
- f. **Lysine Chloride:** Patients will be seen every other day (except for weekends) for laboratory monitoring of electrolytes and renal function to ensure the absence of any adverse effects, and to ensure that the supplement is being taken in the correct manner.
 - i. **Acidosis:** If laboratory results provide any indication of acidification, the dose of lysine chloride will be adjusted (either 2 doses/day, 1 dose/day or 0 dose/day) at the discretion of the study physician and study nephrologist.

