 - ii. **Volume depletion:** Daily lab values will be monitored by the study team. In addition, vital signs will be measured daily. Patients who are admitted at YNHH will additionally be monitored by their treatment teams. Daily lab values will be reviewed by the study physician and nephrologist and, at their discretion, study medication or diuretic dosage may be adjusted.
- g. **Iothalamate meglumine (for patients without a contrast allergy):** The dose administered is the smallest effective dose possible to minimize any medication side effects.
- h. **Iohexol (for patients without a contrast allergy):** The dose administered is the smallest effective dose possible to minimize any medication side effects.
- i. **D₂O:** Deuterium oxide is a safe, natural isotope found in everyone's tap water. It is a frequently used tracers in studies determining TBW. We do not anticipate any risk to the patients from its use.
- j. **Volumex (radiolabeled albumin):** We do not anticipate any significant risks from patients receiving 2 doses of Volumex. This will expose patients to 0.2 rem of radiation, which equals about 8 extra months' worth of natural radiation exposure. Patients under the age of 40 will be given the option of taking a one-time dose of Potassium Iodide to further reduce the risk of radiation exposure from Volumex.

- k. **Potassium Iodide (KI):** To reduce the risks of taking KI, the lowest effective, one-time dose (135 mg) will be administered to patients under the age of 40 who have opted to take this medication to further protect against radiation exposure from Volumex.
- l. **Dextrose 5% Fluid:** The volume of Dextrose 5% will be administered during the blood volume procedures to flush the line and given continuously throughout the study visit only if a KVO fluid is required to keep the IV-line patent. At these volumes, we anticipate the potential of these risks to be minimal. In addition, the participant's vital signs will be measured.
- m. **Imodium AD or Imodium(Loperamide):** This medication is generally well tolerated; it will be administered in smallest effective dose to maximize the benefit of the medication and to minimize any medication side effects. We expect minimal risk by giving the smallest effective dose, initial dose is 4mg and maximum daily dose is 16mg.

9.0 Moderate Risk Data and Safety Monitoring Plan (DSMP) with Data Safety Monitoring Board

(DSMB)

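### Daily venous pH depends on bicarbonate at screening only; a fall below 22 mmol/L on study drug leads to clinical review but to no required pH or closer testing

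*Combined protocol and SAP*

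**What the plan says.** The trigger is in section 4.0, Study Protocol, part B: "If a patient has a serum bicarbonate level less than 22mmol/L at screening, a venous pH and basic blood chemistries will be obtained" each day of the study period, with up to 5 additional safety visits if the patient has left hospital and the tests are indicated. Section 7.4 excludes "Serum bicarbonate level < 20 mmol/L".

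Every patient has one pH before randomisation. At Study Visit 1, "blood will be drawn for determination of venous pH via iSTAT and/or YNHH laboratory", and a value below 7.25 ends participation.

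The protocol also provides a response on treatment. Part B states: "For all patients, the results of any safety tests will be reviewed by the study physician and study nephrologist". Section 8.3 (f.i) adds: "If laboratory results provide any indication of acidification, the dose of lysine chloride will be adjusted", at the discretion of those two clinicians. Section 8.3 (f.ii, on volume depletion) says: "Daily lab values will be reviewed by the study physician and nephrologist".

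Section 8.2 (f.i) describes acidosis as slow to develop and tells the reader: "we will closely monitor serum pH and bicarbonate over the course of the study to be sure this does not occur". It attaches no bicarbonate condition to this.

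**The concern.** Acidosis is the side effect that the protocol singles out for close follow-up. By its own account, it would build up after dosing starts. A trigger read once, before the first dose, cannot respond to that. The plan regards a bicarbonate of 21 mmol/L as low enough for daily pH when it is found at screening. It is silent when the same value is reached on study drug, and it gives no reason for the difference.

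What is at stake is the information given to the clinicians who decide on dose, and how soon they get it. The trigger brings daily chemistries and post-discharge visits as well as pH, so a patient outside it lacks all three as required steps.

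**Working it through.** The plan has no figure to reproduce, so the check is a comparison of every place that deals with pH, bicarbonate, safety laboratory tests or dose adjustment.

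| Place | Applies to | What is required |
|---|---|---|
| 4.0, Visit 1 screening; 7.4 | all | one venous pH before randomisation; below 7.25 stops entry |
| 4.0, part B | bicarbonate below 22 at screening | daily venous pH and chemistries; up to 5 safety visits after discharge |
| 4.0, part D | all, after the switch to oral diuretics | electrolytes and renal function every other day, not at weekends; pH not listed |
| 8.3, f.i | all | dose adjusted if results indicate acidification; no test specified |
| 8.3, f.ii | all, under volume depletion | review of daily laboratory values; pH not named |
| 8.2, f.i | all | pH and bicarbonate monitored closely over the study |

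**Who gets on-treatment pH.** The exclusion below 20 and the trigger below 22 together give an entry band of 20 to <22 mmol/L. In that band pH is daily, which is about 7 tests in a 7-day course. At entry values of 22 or above, the number of required on-treatment pH tests is 0.

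**Two patients with the same result.** Patient A is at 21 mmol/L at screening. Patient B enters at 22 or above and reaches 21 on study drug. Patient A has daily pH, daily chemistries and, after discharge, the extra visits. Patient B has the review and possible dose change in part B and section 8.3, on whatever laboratory results are already due. Under part D, once patient B is on oral diuretics, a result on a Friday has no scheduled follow-up before Monday. The daily values in section 8.3 (f.ii) do not clearly fill this gap, because part D sets a sparser schedule and neither place names pH.

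**Comparison with section 8.2.** Bicarbonate is plausibly followed in everyone through the electrolyte checks, and it is a secondary endpoint. The shortfall is therefore in pH and in the step-up in frequency.

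**Cost of extending the trigger, per newly triggered patient.**
- Draws: the longest course is 8 days. If the first low value comes on day 1, 8 − 1 = 7 daily draws remain, and 7 × 1 cc = 7 cc.
- Relative to study-visit blood: 2 × 100 cc = 200 cc, and 7 / 200 = 3.5%.
- Visits: at most 5 × $25 = $125 at the rate in section 16.1. That section does not say whether its limit of 5 also covers the routine visits in part D, so $125 is an upper limit.

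The documents do not give the share of patients who would cross 22, so no trial-wide total is offered.

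**The case against.** The strongest reply is that the safeguard that matters is already there. For every patient, any sign of acidification leads to a dose decision by the study physician and nephrologist. They can act on bicarbonate alone or order a pH themselves. The protocol sets no on-treatment pH threshold and the fix adds none, so it adds a measurement without a decision rule. The monitoring is also risk-stratified. Section 7.4 excludes low bicarbonate, recent severe acidosis, acidosis-predisposing agents, eGFR below 20 and low urine output. Treatment lasts at most 8 days, and the pilot saw no acid buildup.

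Much of this stands. It is a good argument against daily pH for everyone, which is not proposed. It does not explain why the stratification is applied only at screening. The pilot gives limited reassurance: no events in 10 to 11 patients leaves a one-sided 95% upper limit of 1 − 0.05^(1/10) = 25.9% to 1 − 0.05^(1/11) = 23.8%. Its patients were stable outpatients, and acid buildup was not defined there as bicarbonate below 22.

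Three stronger readings are tempting, and the documents do not support them.
- A reader might infer that an on-treatment fall goes unanswered, or that no pH can be done. Review and dose adjustment cover all patients. What is missing is a requirement for a pH, and nothing forbids one.
- A reader might see two conflicting triggers, because part D mentions "additional safety visits that will be conducted based on serum bicarbonate" without naming screening. That phrase only separates two kinds of visit and refers back to part B. It is a cross-reference to tidy.
- A reader might infer that cases of acidosis would be missed. The documents give no basis for any such number, and the pilot limit does not supply one.

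**Conclusion.** The point holds as a minor to moderate gap in safety monitoring. For a patient who enters at 22 mmol/L or above and then falls below 22 on study drug, the protocol requires neither a pH nor a move to daily chemistries or extra safety visits. Section 8.2, read as written, leads one to expect more. Section 8.2 is a risk description and not a schedule, which softens the mismatch but does not remove it.

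The finding rests on the text alone. The phrase in part B about tests being indicated could be stretched to cover clinical indication, but it most naturally refers to the screening rule and sets no on-treatment threshold. It has not been shown that any particular dosing decision would have been different.

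**What to change.** 1. In section 4.0, part B, replace *at screening* with *at screening or at any time on study drug*. Daily pH and chemistries, and the additional safety visits after discharge, then apply to any patient whose bicarbonate falls below 22 mmol/L.
2. Reword section 8.2 (f.i) to match the schedule actually run: pH at baseline, then daily once bicarbonate is below 22.
3. While amending, repeat the same trigger in part D, state in section 8.3 (f.ii) which patients have daily laboratory values, and confirm that the part D electrolytes include bicarbonate. The trigger cannot work without that result.

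Dose decisions stay with the study physician and nephrologist. The cost is a short amendment plus the per-patient burden worked out above. The assay, the 1 cc draw, the safety visits and their payment are already in the protocol.

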6.1 Genetic Testing & Maintaining Subjects' Privacy

6.2 Types of future research to be conducted using the materials: Subjects' genetic material will be collected for genome sequencing. One of the goals of this study is to determine if variations in human genome influence HF risk, progression and response to treatment. The accrued genetic material from subjects will permit potential future Genome Wide Association Studies (GWAS) regarding the interaction between genetic material and HF disease progression, phenotype and prognosis. No immortalized cell lines or animal studies are planned for this study.

6.3 Plan for collecting materials or the conditions under which material will be received: Subjects' genetic material will be collected and processed at YNHH Park Street clinical laboratory, our study's laboratory facilities at [name], or at YNHH-SRC campus. Each subject's specimens will be processed, labeled with unique study IDs and stored in cryovials in a -80°C freezer.

6.4 Types of Protected Health Information (PHI) about the individual contributors that will be entered into a database: Name, address, telephone number, medical record number (MRN), medical history and allergies, current and past medications and therapies, vital signs, family medical history, results of blood, urine and imaging tests (ex: x-rays, CT scans, MRIs, or ultrasound) and pathology tests (biopsies), DNA, tissue and blood.

6.5 Conditions or procedures for sharing of materials and/or distributing for future research projects: Data collected by the PI and other study personnel listed in this protocol will be distributed for secondary research purposes only after the recipient investigator has obtained HIC approval for the proposed research objective, received an exemption or determination by the HIC the study is not considered human subject research. Data will be distributed for research projects of the same nature and similar purpose specified in this protocol, as agreed to by the subjects by signing the compound informed consent and HIPAA authorization form upon enrollment to the study. The PI is responsible for receiving appropriate attestation by recipient investigators prior to permitting access to the database for activities considered preparatory to research. Attestation will be obtained using the Request for Access to PHI for a Research Purpose Form found at <http://www.yale.edu/hrpp/forms-templates/hipaa.html>.

6.6 Widespread sharing of materials: Samples and data collected during the research study will be shared with other investigators for research projects of the same nature and similar purpose specified in this protocol, as described above.

6.7 Stripping materials of all identifiers: Samples will be immediately stripped of all identifiers, and given a unique study ID as soon as deposited in the AVA-HF bio-repository.

6.8 Can donor-subjects withdraw their materials at any time, and/or withdraw the identifiers that connect them to their materials? Yes; researchers may still use the material or data that was collected before the subject withdrew permission/authorization in order to complete the research that has already commenced. All specimens and data retained in the AVA-HF biorepository will be destroyed upon receiving notice of a subject's withdrawal of permission for continued use of their specimens.

6.9 Provisions for protecting participants' privacy: The PI will ensure patients' anonymity is maintained. Each subject is assigned a unique study identification number and is tracked

through this number. Subjects' clinical data will be entered into password protected software and stored on a secure server. A log of subjects' names, subject ID numbers and pertinent registration information (ex: address, phone number and emergency contact information) is maintained on a password-protected computer, to allow reidentification of subjects when necessary.

6.10 Methods for the security of storage and sharing of materials: Specimens are labeled only with unique study ID numbers. When certain samples are shipped and analyzed by appropriate collaborating laboratories, samples will be sent anonymously, ensuring laboratories will not have access to any clinical or phenotype data, thus assessments will be made in a blinded fashion. The specific laboratories will vary depending on the biochemical test performed; specimens may be analyzed at individual or core laboratories, academic institutions or industry collaborators.

